### 16.2 Demographic and Baseline Characteristics

The demographic information that will be collected: Age, parity, race/ethnicity. At the initial visit, we will also collect: date of service, gestational age by ultrasound and date of ultrasound, past medical history, current medications, blood pressure, weight, height, and medications prescribed or dispensed. All participants will receive the same dose of Mifeprex®.

### 16.3 Analysis of Primary Endpoint

Feasibility of the pharmacy dispensing model will be assessed in quantitative descriptive analyses of satisfaction variables from the pharmacists' end line survey (overall satisfaction, perceived benefits/challenges, and ease of implementation of pharmacy dispensing) using chi-square and *t* tests where appropriate. We will also calculate the proportion of pharmacists who refused to dispense Mifeprex® during the study. In addition, feasibility will be assessed in qualitative analyses of open ended interviews with pharmacists about dispensing Mifeprex® in pharmacies.

### 16.4 Analysis of Secondary Endpoints

Acceptability and satisfaction with the pharmacy dispensing model among patients will be assessed primarily through surveys with patient participants using quantitative and qualitative analyses. The particular Day 2 survey variables we will analyze include those on overall satisfaction with the pharmacy, reasons for dissatisfaction, and perceptions about the wait time, the way the patient was treated and the information she received. Clinical outcomes, including effectiveness and adverse events, with pharmacist-dispensed mifepristone will be assessed using quantitative data abstracted from patient medical records, as well as information on clinical outcomes captured in the Day 14 patient survey. Pharmacist knowledge about medication abortion before and after the intervention will be assessed through quantitative analyses of surveys completed by the pharmacists.

Adverse event rates will be coded by body system and MedDra classification term. Adverse events will be tabulated and will include the number of patients for whom the event occurred, the rate of occurrence, and the severity and relationship to study drug.

## 16.5 Interim Analysis

No interim analysis is planned. Unexpected and serious adverse events will be monitored as noted above (see section 12).

## 16.6 Sample Size

We aim to recruit 350 patients for this pilot study, which is a feasible sample at the study sites. With a sample size of 350, if the proportion of patients with a complete abortion is 95%, the 95% confidence interval of that proportion will be  $\pm 2.7\%$ . Abortion completion is an important clinical outcome.

We aim to survey all the pharmacists at the study sites, up to 50. This sample size will be determined by the number of pharmacists at the study sites. We have confirmed that there is at least one pharmacy at the site who is willing to dispense mifepristone, which is sufficient for the study. In the unlikely event that a willing and trained pharmacist is not on site to dispense the medication, the patient will be told when she can return to the pharmacy to have the prescription filled. Alternatively, the patient may return to the clinic, where the mifepristone will be dispensed. If that happens, the study will still cover the cost of the medication abortion, but the patient will be discontinued from the study.

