If a patient is unable to obtain the medications from the pharmacy, for whatever reason, the patient will be referred back to the clinic, where the mifepristone will be dispensed. If a rare patient must return to the clinic to receive the mifepristone or other drugs, she will not be removed from the study and will be included in the analysis per the "intention-to-treat" principle.

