## 10.5 Data Abstraction

As noted above in section 9, de-identified data about the clinical visits of participants consenting for the study will be abstracted from the electronic medical record system of the participating sites. This includes clinical information including demographics (age, parity, race, ethnicity), initial visit information (date of service, gestational age, past medical history, medications, laboratory values), and follow-up visit information (date of service, treatment given, symptoms, outcome of abortion, adverse events, and other follow-up care). The site PI will perform a chart review for each participant 6 weeks after enrollment. De-identified data will be entered into a Qualtrics or REDCap electronic form (see Appendix G for the variables that will be abstracted). As noted above, the site PI will supervise the data abstraction and replace the participant name with the Study ID prior to transferring the data to the UCSF research team.

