### 13.3 Replacement of Subjects

If any subject withdraws or does not complete the study as planned, they will be replaced with an additional participant.

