### 16.1 Data Sets Analyzed

All eligible patients who receive the dose of the study drug will be included in the analysis. All eligible pharmacists who complete at least one survey or interview will be included in the pharmacist analysis.

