Secondary objectives include assessing patient satisfaction with the pharmacy-dispensing model; describing clinical outcomes, including effectiveness and adverse events, with pharmacist-dispensed Mifeprex®; and comparing pharmacist knowledge about medication abortion before and after the intervention.

3. Analyses

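### Sections 6.1 and 16.6 give opposite study status to a patient who gets mifepristone at the clinic because no willing, trained pharmacist was on site

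*Protocol*

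**What the plan says.** **Protocol 6.1 (Study Population)** sets a general rule: "If a patient is unable to obtain the medications from the pharmacy, for whatever reason, the patient will be referred back to the clinic", where mifepristone is dispensed. Of such a patient it says "she will not be removed from the study and will be included in the analysis", and it invokes intention to treat.

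**Protocol 16.6 (Sample Size)** takes one cause, the absence of a willing and trained pharmacist. The patient is told when she can come back to the pharmacy, or she may return to the clinic and receive the drug there. For the clinic route: "If that happens, the study will still cover the cost of the medication abortion, but the patient will be discontinued from the study".

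**Protocol 16.1 (Data Sets Analyzed)** defines the patient set: "All eligible patients who receive the dose of the study drug will be included in the analysis". It sets no condition on where the drug was dispensed and does not mention discontinuation.

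**Protocol 13.3 (Replacement of Subjects)** says: "If any subject withdraws or does not complete the study as planned, they will be replaced with an additional participant". It does not say whether the replaced person's data are kept.

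**The SAP** defines no patient analysis set and has no rule for patients given the drug at the clinic.

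**The concern.** The study asks whether pharmacy dispensing works. A patient sent back to the clinic because nobody at the pharmacy could or would dispense is a failure of that model. If she is discontinued and then replaced, the failure may leave the follow-up while a patient who was served takes her place.

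The results exposed are secondary and patient-level, chiefly satisfaction with the pharmacy on Day 2 and the overall experience on Day 14. Losing people whom the model did not serve would tend to make it look better. There are six sites, and each could follow a different section, so the denominator would depend on which one the staff had read.

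**Working it through.** The plan gives no figure on this point, so there is none to reproduce. The contradiction is a matter of text; the arithmetic only bounds its effect.

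**1. Do the two rules reach the same patient?**
- Trigger: any inability to obtain the drugs (6.1); no willing, trained pharmacist on site (16.6). The second is a case of the first.
- Route: the clinic dispenses mifepristone, in both.
- Status: stays in the study (6.1); discontinued (16.6).

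The statuses cannot both hold.

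**2. Does other text settle it?**
- Inclusion in the analysis: 6.1 includes her, and 16.1 does so if she receives the dose. Section 16.6 does not mention analysis. Section 16 says the SAP will carry any modification of the analysis plan, and the SAP carries none here. On this the documents agree well enough.
- Study status: no other section decides it. Section 13.3 would apply to her if she is discontinued, since she would not have completed as planned.
- Data at risk: section 10.5 says "The site PI will perform a chart review for each participant 6 weeks after enrollment", and the six-week collection of serious adverse events in 12.2.1 makes no exception for discontinued patients. That leaves the Day 2 and Day 14 surveys as the most exposed.

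**3. How far could Day 2 satisfaction move?** SAP 3.1 reports the proportion very satisfied. Let n be the respondents with affected patients kept, f the number affected, p the proportion very satisfied among the others, and m the proportion among the affected.

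- Kept: [p(n − f) + m f]/n = p + f(m − p)/n
- Dropped: p
- Difference: f(m − p)/n, so at most f/n in size. If the dropped patients are replaced by others with proportion r, the difference is f(m − r)/n, with the same bound.

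Per patient the bound is 1/n: 1/350 = 0.29 points if all 350 planned patients respond, and 1/280 = 0.36 points under an assumed 80% response (0.80 × 350 = 280).

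Illustration with m = 0, where the gap is p f/n. The values of f, p and the response rate are assumptions, because the documents give none:

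| n | f | bound f/n | gap, p = 0.65 | gap, p = 0.90 |
|---|---|---|---|---|
| 350 | 1 | 0.29 | 0.19 | 0.26 |
| 350 | 4 | 1.14 | 0.74 | 1.03 |
| 280 | 4 | 1.43 | 0.93 | 1.29 |

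(percentage points)

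The gaps in the last two columns need each affected patient to answer the item and to be less than very satisfied. If she leaves it blank, keeping her does not move this percentage at all.

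**4. Abortion completion.** Take the plan's 95% in the other 346 patients and suppose 4 affected patients complete at 80% or at 100% (assumed). The estimate with them kept is (346 × 0.95 + 4 × 0.80)/350 = 94.83% or (346 × 0.95 + 4 × 1.00)/350 = 95.06%, against 95.00% without them. The shift can go either way, and nothing in the documents says which.

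**The case against.** A reader might infer that 16.6 removes these patients from the analysis. It does not say so. It sits under sample size and speaks of study status only, while 6.1 and 16.1, which do address the analysis, both point to inclusion.

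A reader might also take the wording of 16.4, outcomes "with pharmacist-dispensed mifepristone will be assessed using quantitative data abstracted from patient medical records", or of the SAP objectives, "describing clinical outcomes, including effectiveness and adverse events, with pharmacist-dispensed" Mifeprex®, as an exclusion rule. The SAP describes the whole cohort in those terms, so the phrase names the model and does not define who is analysed. Nor do the documents support a claim of bias in abortion completion or in the primary outcomes. The latter come from pharmacist surveys and from refusals reported by pharmacy managers, site staff and the pharmacists themselves.

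The harm also needs several steps. She must take the clinic route and not return to the pharmacy later. Discontinuation must mean that her surveys are not collected or not used. Section 10.2 sends the Day 2 link the next day and encourages even women who decide not to proceed to answer, so losing that survey is not certain. Section 8.1 deals with known staffing gaps before the patient leaves, or does not enrol her, and the protocol calls the event rare and unlikely. Even the largest illustrated gap, 1.29 points, is below the sampling error at that size: 1.96 × √(0.90 × 0.10/280) = 3.5 points.

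All of this limits the consequence, and it stands. It does not remove the conflict over status. Unforeseen absences remain possible, and 16.6 itself provides for them. Tracking refusals by pharmacist does not count the patients affected.

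**Conclusion.** The contradiction is certain: 6.1 keeps a patient whom 16.6 discontinues, and no other text decides between them. The open question is narrow, namely whether her surveys are collected and whether she is replaced. Inclusion in the analysis is largely settled by 6.1 and 16.1.

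If 16.6 is followed, some failures of the model may be missing from the secondary patient results, mainly satisfaction. The direction, favourable to the model, rests on the reasonable but undocumented expectation that patients who were not served would be less satisfied. The size is unknown and probably small: at most 1/n per affected patient, with no rate given. This ranks between a minor point and one that should be fixed. The case for acting is that the correction is cheap and the protocol already states the rule in 6.1.

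**What to change.** 1. In 16.6, delete the clause that discontinues the patient, so that it agrees with 6.1 and she stays in follow-up and in the analysis. This concerns study status only; dispensing and care are unchanged.
2. In 13.3, state that the available data of replaced participants stay in the analysis. In 16.1 or the SAP, state that patients are analysed wherever the drug was dispensed, and tabulate place of dispensing.
3. Show Day 2 pharmacy satisfaction separately for patients not served at the pharmacy, because the SAP item asks about the pharmacy visit at which the pill was obtained and does not fit someone who obtained it at the clinic. A sensitivity analysis counting them as not very satisfied is optional.

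The cost is a few sentences and one extra tabulated variable. The Investigational Drug Accountability Log (8.4, 8.5) already records what each pharmacy dispenses, and the medical record (9.1.3) what was prescribed or dispensed at the initial visit. Reported satisfaction may come out slightly less favourable.

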# 17 DATA COLLECTION, RETENTION AND MONITORING

## 17.1 Data Collection Instruments

Survey data will be collected directly from medication abortion patients using an online survey at Day 2 and Day 14 following the medication abortion. Clinical data will also be abstracted from the electronic medical record system at each study site. Pharmacists will be invited to complete a survey and interview prior to the initiation of mifepristone dispensing, as well as at the end of the study. All study instruments will be submitted for review prior to initiating data collection.

Study Population	Study instruments	Consent forms
Medication abortion patients	Day 2 survey Day 14 survey Clinical data abstraction form	Patient informed consent (written) HIPAA Authorization Form
Pharmacists	Baseline survey Baseline interview guide End-line survey End-line interview guide	Pharmacist informed consent for survey and interview (click-through or verbal)

## 17.2 Data Management Procedures

Survey data will be collected in Qualtrics, an online survey software. The UCSF research team will

access it securely through a protected account. Participants' personal identifiers (including first name and last initial, phone number and email address) will be collected and stored separately from clinical, survey, and interview data. At Kaiser, only email address will be collected by UCSF; Kaiser staff will manage any in-person and phone contact with participants.

Clinical information (including date of clinic visit/s, success of the abortion, and adverse events) will be extracted from the electronic health record. These data will be de-identified, linked with a unique study ID, and entered into a Qualtrics or REDCap electronic form by the study site.

Interview data will be audio-recorded, transcribed and imported into the analysis software. Identifiers will be stored separately.

### 17.3 Data Quality Control and Reporting

The UCSF study team will train sites on standardized recruitment and consent procedures and have regular communication with study clinics and pharmacies to provide technical assistance and check on the progress of the study. Data collection tools and procedures will be pilot tested before implementation. Data will also be monitoring periodically to ensure that data collection, coding, and management procedures are being conducted according to protocol and ethical guidelines.

Survey data gathered through Qualtrics, an online survey software, will be secure and HIPAA compliant. Because of its high level of data security, it is the recommended survey software for UCSF research. Data are collected and stored on a secure server and scanned regularly to ensure vulnerabilities are quickly found and patched. UCSF will also take special precautions to collect and store personal identifiers separately from research data on password protected secure accounts, using encrypted, physically secure computers and devices. Results will be presented in aggregate and will not share identifying information about participants.

### 17.4 Archiving of Data

The database is safeguarded against unauthorized access by established security procedures; appropriate backup copies of the database and related software files will be maintained. Databases are backed up by the database administrator in conjunction with any updates or changes to the database.

Surveys, interview recordings, transcripts, and forms will be stored in a locked cabinet at the study site and on computers only accessible by core members of the research team. When these procedures are followed, it is highly unlikely that any of the information revealed by participants during the course of the interviews will be disclosed to anyone outside the research team.

### 17.5 Availability and Retention of Investigational Records

The site PI must make study data accessible to authorized representatives of the PI (or designee), IRB, and Regulatory Agency (e.g., FDA) inspectors upon request. A file for each subject must be maintained that includes the signed Informed Consent and copies of all source documentation related to that subject. The site PI must ensure the reliability and availability of source documents.

All study documents (patient files, signed informed consent forms, etc.) will be kept secured for a period of two years following the completion of the study.

### 17.6 Monitoring

Site-specific periodic monitoring visits at the sites will be undertaken for study audits as part of our plan to assure quality. The monitor, consisting of the PI and/or his designee from the UCSF research team, will also provide monitoring reports promptly following each visit and present this information to the site PI.

## 17.7 Subject Confidentiality

In order to maintain subject confidentiality, only a site number, subject number and subject initials will identify all study subjects on documentation.

Potential participants will have the option of not participating in any part of the study, including any part of the interview (pharmacists), and they may refuse to be audio-recorded during the interview, without any adverse consequences for their medical treatment (patients) or employment (pharmacists). Attempts to contact participants will be limited and should a message be left for the woman on her voicemail, no information related to the details of her study participation or nature of her care will be recorded. If at the time the woman is reached, she wishes to reschedule contact at a more appropriate or convenient time, staff will be flexible and accommodating, particularly to safeguard confidentiality.

All interviews with pharmacists will be conducted in a private area or private room designated for this purpose at the study sites or at another mutually agreed upon location. No identifying information will be included on the audio recording of the interview.

## 18 ADMINISTRATIVE, ETHICAL, REGULATORY CONSIDERATIONS

The study will be conducted according to the Declaration of Helsinki, Protection of Human Volunteers (21 CFR 50), Institutional Review Boards (21 CFR 56), and Obligations of Clinical Investigators (21 CFR 312).

To maintain confidentiality, all data collection forms will be identified by a coded number and initials only. All study records will be kept in secured files only accessible to the UCSF or site-specific research team. Data with patient identifiers used for contact purposes will be stored separately from survey/interview responses. Any paper forms will be stored in a locked file cabinet. Clinical information will not be released without written permission of the subject, except as necessary for monitoring by the FDA. The PI and site PIs must also comply with all applicable privacy regulations (e.g., Health Insurance Portability and Accountability Act of 1996, EU Data Protection Directive 95/46/EC).

### 18.1 Protocol Amendments

Any amendment to the protocol will be written by the PI. Protocol amendments cannot be implemented without prior written IRB approval except as necessary to eliminate immediate safety hazards to patients. A protocol amendment intended to eliminate an apparent immediate hazard to patients may be implemented immediately, provided the IRBs are notified within five working days.

### 18.2 Institutional Review Boards and Independent Ethics Committees

The protocol and consent form will be reviewed and approved by the UCSF IRB, as well as the University of Washington IRB and Kaiser IRB, prior to study initiation. Serious adverse experiences regardless of causality will be reported to the IRB in accordance with the standard operating procedures and policies of the IRB, and the Investigator will keep the IRB informed as to the progress of the study. The Investigator will obtain assurance of IRB compliance with regulations.

Any documents that the IRB may need to fulfill its responsibilities (such as protocol, protocol amendments, consent forms, information concerning patient recruitment, payment or compensation procedures, or other pertinent information) will be submitted to the IRB. The IRB written unconditional approval of the study protocol and the informed consent form will be in the possession of the PI and site PI before the study is initiated. This approval must refer to the study by exact protocol title and number and should identify the documents reviewed and the date of review.

Protocol and/or informed consent modifications or changes may not be initiated without prior written IRB approval except when necessary to eliminate immediate hazards to the patients or when the change(s) involves only logistical or administrative aspects of the study. Such modifications will be submitted to the IRB and written verification that the modification was submitted and subsequently approved should be obtained.

The IRB must be informed of revisions to other documents originally submitted for review; serious and/or unexpected adverse experiences occurring during the study in accordance with the standard operating procedures and policies of the IRB; new information that may affect adversely the safety of the patients of the conduct of the study; an annual update and/or request for re-approval; and when the study has been completed.

### 18.3 Informed Consent Form

Informed consent will be obtained in accordance with the Declaration of Helsinki, ICH GCP, US Code of Federal Regulations for Protection of Human Subjects (21 CFR 50.25[a,b], CFR 50.27, and CFR Part 56, Subpart A), the Health Insurance Portability and Accountability Act (HIPAA, if applicable), and local regulations.

The consent form must be approved by the IRB. The written consent document will embody the elements of informed consent as described in the International Conference on Harmonisation and will also comply with local regulations.

Participants will be given information about the study and their rights as part of the informed consent process. On agreeing to participate, they will be asked to sign an informed consent form. For patients, the form will seek consent both for obtaining clinical data from medical records, as well as for participation in the online or telephone surveys. Medical record data will only be abstracted from patients who also provide consent using the HIPAA Authorization form. Pharmacists will be consented for their participation in the survey and interview separately; for the survey, the consent will be a click-through consent on the online platform and for the interview the consent will be verbal. As part of this informed consent process, potential participants will be informed of: (1) the purpose and methods of the study, (2) alternatives to participation in the study, (3) procedures to protect confidentiality, (4) the right to withdraw from the study at any time, (5) the fact that participation or non-participation will not affect the medical care that they receive, and (5) persons to contact for any questions about the study. The participants will also be given names and phone numbers of persons to contact with any questions regarding the study.

